9.2 Specific Aim 1b Analysis

Aim 1b completes the efficacy trial by doubling the size of the analytical sample and allowing for highly accurate specification of observed treatment effects; it is a single-arm, pooled (i.e., ID+DD) observed treatment effects analysis whereby data points from the ID arm are paired with their analytical comparators from the DD arm (i.e., ID enrollment data with DD 1-month post-enrollment data; ID 1-month post-enrollment data with DD 2-months post-enrollment data);

the proposed analytical model provides increased analytical power for HIV subgroup and/or contingency analyses, given the greater number of persons receiving the intervention relative to the proposed RCT model (i.e., N=300 receiving the app). Power Calculations for Specific Aim 1b: estimated pre-/post-test observed treatment effect MDEs for HIV Prevention or Care Continuum outcomes related to Specific Aim 3b are: 1) Di—OR = 1.61; 2) Cu—IRR= 1.35; for methamphetamine use outcomes: 1) Di—OR = 0.59; 2) Cu—IRR = 0.89; 3) Co—f2 = 0.01; for HIV sexual risk outcomes: 1) Di—OR = 0.63; 2) Cu—IRR = 0.85; 3) Co—f2 = 0.01.

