1.0 STUDY OBJECTIVES

1.1 Specific Aims

- 1.1.1 Specific Aim 1a: Conduct a RCT to evaluate reductions of methamphetamine use and HIV sexual risk behaviors, and increased advancement along the HIV Prevention or Care Continuum using a two-arm RCT to determine intervention effects through comparison of the Immediate Delivery [ID] (n=150) and Delayed Delivery [DD] (n=150) arms.
- 1.1.2 Specific Aim 1b: Evaluate reductions in methamphetamine use and HIV sexual risk behaviors, and increased advancement along the HIV Prevention or Care Continuum using an observed treatment effects analysis powered for prospective sub-group analyses to compare longitudinal pre/post data from the pooled ID and DD arms (n=300);
- 1.1.3 Specific Aim 1c: Evaluate reductions in methamphetamine use and HIV sexual risk behaviors, and increased advancement along the HIV Prevention or Care Continuum using a two-arm historical matched comparison design to evaluate the outcomes of the *Getting Off* app (ID+DD; n=300) relative to a matched sample of participants having previously attended the brick-and-mortar group-based *Getting Off* intervention (n~600; total n=900).

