3.0 STUDY DESIGN

3.1 Overview

Getting Off App is a randomized controlled trial to assess the impact of *Getting Off*, a culturally competent Cognitive Behavioral Therapy-based app for reducing methamphetamine use, HIV sexual risk behaviors, and increase advancement along the HIV Prevention or Care Continuum, with the desired outcome of significant reductions in methamphetamine use and HIV sexual risk behaviors as well as increased odds of advancement along the HIV Prevention or Care Continuum among MSM, aged 18-65, who report using methamphetamine within the past year. The design of *Getting Off* App is illustrated in Figure 1.

Figure 1: Getting Off App Study Design

Figure 1: RCT Design

Aim1a: Efficacy Trial - Two-arm RCT to determine intervention effects through comparison of ID and DD arms.

Aim1b: Efficacy Trial - Observed treatment effects analysis to compare pre/post data from the pooled ID and DD arms.

Aim1c: Non-inferiority Trial - A historical matched comparison design to evaluate the outcomes of the Getting Off app (ID + DD) to a historical matched sample of participants who attended the brick-and-mortar Getting Off intervention.

Following screening, informed consent and baseline assessments, participants will be randomized into one of two arms: Arm A: Immediate access to the Getting Off app (Immediate Delivery [ID]); or, Arm B: Participants will have access to the Getting Off app after a delayed 30-day period (Delayed Delivery [DD]). Participants in both arms will receive the same Getting Off app and participants in both arms will be given 30-days to complete the 24 sessions; it is expected to take far less time to progress through the self-directed app than the group-based intervention. The randomized two-arm repeated measures design will assess participants at 1-, 2- (DD arm only), 3-, 6-, and 9-months post-randomization to determine longitudinal intervention effects, observed treatment effects, and a historical comparison with a matched sample of participants who have attended the brick-and-mortar group-based Getting Off intervention (see Figure 1). The study will use an “intent-to-treat” design; participants will be assessed regardless of participation or retention.

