9.0 ANALYTIC APPROACH

9.1 Specific Aim 1a Analysis

Aim 1a, which begins the efficacy trial, is a two-arm, non-blinded RCT whereby half of all participants are randomly assigned to receive the Getting Off app immediately (ID arm; n=150; equivalent to an “active intervention” arm) and half are randomly assigned to receive the app after a 30-day delay (DD arm; n=150; equivalent to a “control” arm). The proposed analytical model allows for causal analysis of intervention effects. Power Calculations for Specific Aim 1a: estimated RCT MDEs for HIV Prevention or Care Continuum outcomes related to Specific Aim 1a are: 1) dichotomous (Di)—Odds Ratio (OR) = 1.97; 2) counted (Cu)—Incidence Rate Ratio (IRR) = 1.51; 3) continuous (Co)— f^2 = 0.03; for methamphetamine use outcomes: 1) Di—OR = 0.48; 2) Cu—IRR = 0.85; 3) Co— f^2 = 0.05; for HIV sexual risk behaviors outcomes: 1) Di—OR = 0.52; 2) Cu—IRR = 0.78; 3) Co— f^2 = 0.05.

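### Aim 1b is an uncontrolled pooled pre/post change labelled as efficacy evidence, and it omits the delayed arm's change over its waiting month

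*Combined protocol and SAP*

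**What the plan says.** Section 9.2 (Specific Aim 1b Analysis) opens with "Aim 1b completes the efficacy trial by doubling the size of the analytical sample". It then defines the analysis: "it is a single-arm, pooled (i.e., ID+DD) observed treatment effects analysis". The data points are aligned on app access: "ID enrollment data with DD 1-month post-enrollment data; ID 1-month post-enrollment data with DD 2-months post-enrollment data". Both members of each pairing come from participants at the same stage of app access, so neither serves as a control for the other. DD enrolment is not among the listed points.

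Figure 1 in Section 3.1 repeats the label: "Aim1b: Efficacy Trial - Observed treatment effects analysis to compare pre/post data from the pooled ID and DD arms". Section 1.1.2 also describes a pre/post comparison of the pooled arms, and gives power for sub-group analyses as a purpose.

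Section 9.1 (Specific Aim 1a Analysis) treats the DD arm during its 30-day delay as the control, and there states: "The proposed analytical model allows for causal analysis of intervention effects". Section 8.1 specifies mixed effects GLMs. Its covariates are diagnostic, psychosocial, barrier/facilitator and sociodemographic variables; it names no term for time since enrolment or for the waiting period. Section 8.3 bases all power calculations on two time points.

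**The concern.** A single-arm pre/post test cannot separate the app from anything else that changes after enrolment, such as regression to the mean, repeated assessment or elapsed time. The protocol supplies plausible sources. Both arms have a 60 to 90 minute baseline assessment (Section 6.3) and baseline HIV and STI testing with referral (Section 6.6.3), whether or not they have app access.

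Such change enters Aim 1b unevenly. For ID, the first 30 days after enrolment fall inside the pre/post window. For DD they fall before the pre value. The DD enrolment-to-month-1 change would show how large this drift is, but Aim 1b does not use it.

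At stake is what the trial may conclude. A result headed as efficacy, with 300 participants and a narrower interval than the randomised comparison, could be read as the stronger evidence although it has no control.

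**Working it through.** **1. Inputs from the documents.** Two-sided alpha 0.05 and power 0.80 (Section 8.3). Methamphetamine use 80% in the DD pre-intervention period (Section 8.2). Detectable ORs for dichotomous use of 0.48 in Aim 1a (Section 9.1) and 0.59 in Aim 1b (Section 9.2).

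**2. The plan's own figures.** Power for two independent proportions with n per group:

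Φ{ [ |p1 − p2|√n − 1.96√(2p̄(1 − p̄)) ] / √(p1(1 − p1) + p2(1 − p2)) }

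- Aim 1b: odds 4 × 0.59 = 2.36, so p2 = 2.36/3.36 = 0.702. With 300 pre and 300 post observations, power is 79.1%.
- Aim 1a: odds 4 × 0.48 = 1.92, so p2 = 1.92/2.92 = 0.658. With 150 v 150, power is 79.6%.

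Both stated ORs reproduce, so there is no arithmetic error here. The Aim 1b figure comes from counting 300 uncontrolled pre and 300 post observations. At OR 0.59 the randomised 150 v 150 comparison has 49.8% power.

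**3. Aim 1b when the app does nothing.** Assumptions: 80% use at enrolment in both arms, pre/post correlation 0 to 0.5, and the drifts below. Pooled pre is the mean of the enrolment and month-1 proportions; pooled post is the mean of months 1 and 2. With b and c the probabilities of changing from use to non-use and the reverse, d = b − c and s = b + c, McNemar-type power for 300 pairs is

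Φ{ (d√300 − 1.96√s) / √(s − d²) }

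Example, one-off 10-point fall: pre 0.75, post 0.70, d = 0.05, OR = (0.70/0.30)/(0.75/0.25) = 0.78.
- Correlation 0: s = 0.400, so (0.866 − 1.240)/0.630 = −0.59, which gives 28%.
- Correlation 0.5: s = 0.203, so (0.866 − 0.884)/0.448 = −0.04, which gives 48%.

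| Use at months 0, 1, 2 without any app effect | Pooled pre, post | OR | Aim 1b significant |
|---|---|---|---|
| 80, 80, 80% | 80, 80% | 1.00 | 5% |
| 80, 75, 75% | 77.5, 75% | 0.87 | 11–17% |
| 80, 70, 70% | 75, 70% | 0.78 | 28–48% |
| 80, 70, 60% | 75, 65% | 0.62 | 76–96% |

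The 5% in the first row comes from simulation. The randomised month-1 comparison of Aim 1a rejects about 5% in every row, because both arms drift alike.

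**4. What an adjusted model would deliver.** Generalised least squares for ID (months 0, 1) and DD (months 0, 1, 2), n = 150 each, constant within-person correlation 0.5, in outcome SD units:

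- Uncontrolled pre/post: √(2(1 − 0.5)/300) = 0.058.
- Aim 1a adjusted for baseline: √(2(1 − 0.25)/150) = 0.100.
- App-access term with free month effects: 0.100.
- App-access term with a linear trend: 0.099.
- App-access term with a single step after enrolment: 0.075.

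**The case against.** Much can be said for the plan. It openly calls Aim 1b single-arm and observed, places its explicit causal statement under Aim 1a, and justifies pooling partly by power for HIV subgroups. A reader might infer that the waiting month is wasted, or that the plan claims a causal effect from Aim 1b. The documents support neither: the waiting month is the Aim 1a control, its endpoint is the DD pre value in Aim 1b, and only the DD enrolment-to-month-1 change is omitted, from Aim 1b alone.

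The drifts are assumed and all run one way. A rise in use would hide a benefit instead. Eligibility requires only use within 365 days, so selection on a recent high value may be weak. The 80% is stated for the DD pre-intervention period, not for enrolment in both arms.

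The pairing also gives some protection. With a one-off 10-point fall, measuring everyone from enrolment would give OR (0.70/0.30)/(0.80/0.20) = 0.58 and reject 81 to 98% of the time, against 0.78 and 28 to 48% as planned.

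Finally, an adjusted model may only repeat Aim 1a. With free month effects it does, because nobody is unexposed at month 2.

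These points limit the concern without removing it. The efficacy wording remains in two places, no adjustment or caveat accompanies it, and the partial protection does not bring rejection to 5% under drift.

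**Conclusion.** The point holds as one of labelling and missing adjustment. Aim 1b measures change from before to after app access, whatever its cause, and the plan nevertheless counts it towards efficacy. Its smaller detectable effect (OR 0.59 against 0.48) describes precision for that mixed quantity; it adds no power for a controlled app effect.

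The rejection rates (11 to 17% for a one-off 5-point fall, 28 to 48% for a one-off 10-point fall, 76 to 96% for a steady 10-point fall per 30 days, 5% for none) rest on assumed drifts, 80% use at enrolment and correlation 0 to 0.5. They illustrate the mechanism. It would be too strong to infer that this trial will report a false efficacy finding: the documents give no natural 30-day change, and the randomised Aim 1a is unaffected.

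**What to change.** 1. In Section 9.2 (Aim 1b) and Figure 1, remove the statement that Aim 1b completes the efficacy trial and its efficacy label. State that Aim 1b is descriptive or supportive and that the efficacy conclusion rests on randomised Aim 1a. Say in Section 9.2 and in the Model 2 column of Table 2 that the Aim 1b detectable effects refer to uncontrolled pre/post change.
2. As a supporting analysis, fit one mixed model to ID months 0 and 1 and DD months 0, 1 and 2, with an app-access term and a time term whose form is fixed in advance. Report the app term beside the plain pre/post change. State that free month effects give the same precision as Aim 1a (SE 0.100 SD at correlation 0.5), that a linear trend gives 0.099, and that 0.075 requires assuming no drift after month 1. The data cannot separate such drift from the app effect at month 2. These SEs are for a continuous outcome, so the precision for binary outcomes needs its own calculation.

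Cost: a few restated sentences and one model on data already scheduled for collection. The adjusted interval will be wider than the uncontrolled one (SE 0.058). Pooled subgroup analyses can stay, with the same descriptive status.

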9.2 Specific Aim 1c Analysis

Aim 1c provides a non-inferiority trial against the group-based, brick-and-mortar intervention upon which the app is based, and will be a historical matched comparison analysis whereby pooled data from the proposed study (i.e., ID+DD, N=300) is contrasted against historical data from participants who have attended the brick-and-mortar Getting Off intervention after 2012 (N~600; matched according to age, race/ethnicity, and HIV status [see Random Assignment]). The proposed analytical model allows for non-inferiority analyses comparing the relative efficacies of brick-and-mortar vs. mHealth delivered intervention content. Power Calculations for Specific Aim 1c: estimated historical matched comparison MDEs for HIV Prevention or Care Continuum outcomes related to Specific Aim 3c are: 1) Di—OR = 1.52; 2) Cu—IRR = 1.30; 3) Co—f2 = 0.01; for methamphetamine use outcomes: 1) Di—OR = 0.62; 2) Cu—IRR = 0.90; 3) Co—f2 = 0.01; for HIV sexual risk outcomes: 1) Di—OR = 0.66; 2) Cu—IRR = 0.87; 3) Co—f2 = 0.01.

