2.0 INTRODUCTION

2.1 Rationale

Methamphetamine use among MSM is associated with increased rates of HIV prevalence and transmission, as well as substandard advancement along the HIV Prevention and Care Continua. Methamphetamine use among MSM is deeply integrated into socio-sexual networks including the use of smartphone apps and websites to find sexual partners. Given the growth of mobile health technology, it is no longer necessary or reasonable to limit methamphetamine treatment options to physical sites, clustered in urban areas, and administered using generic, non-tailored content. The project builds upon the established efficacy of our manualized methamphetamine-use treatment intervention, “*Getting Off: A Behavioral Treatment Intervention for Gay and Bisexual Male Methamphetamine Users*,” and the highly promising findings from the successful Stage I proof-of-concept study, to complete translation of *Getting Off* into a cross-platform (iOS and Android) app and assess the app’s efficacy *and* non-inferiority in a scientifically rigorous randomized trial. The *Getting Off* app, like the group-based intervention before it, will use the principles of Cognitive Behavioral Theory and Stages of Change to help MSM reduce or eliminate methamphetamine use and HIV sexual risk behaviors, and increase advancement along the HIV Prevention or Care Continuum (including uptake of HIV testing, pre-, and post-exposure prophylaxis [PEP/PrEP] and PrEP adherence and persistence for those who are HIV negative; ART uptake and adherence for those who are HIV positive).

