8.0 STATISTICAL ANALYSES

8.1 General Analytical Approach

All primary outcomes are operationalized and assessed in at least two discrete ways, increasing accuracy of measurements, reducing concerns of fully missing data, and allowing for post-hoc comparisons of concurrent validity across assessment modalities (see Table 2 for all outcome operationalizations). Descriptive statistics will be calculated and provided for all outcomes, with specific metrics chosen based on the distributional properties of each variable (e.g., counts and percentages for nominal variables; means and standard deviations for parametric continuous variables; ranges and medians for non-parametric continuous variables). Diagnostic (i.e., DSM-5), psychosocial (e.g., URICA), barriers and facilitators (e.g., housing insecurity, lack of transportation), and/or sociodemographic variables will be tested for significant association with study outcomes (i.e., advancement through the HIV Prevention or Care Continuum, methamphetamine use, HIV sexual risk behaviors), with specific tests of association chosen based on the distributional properties of the outcome variables in question. All variables demonstrating significant statistical association with one or more of the study outcomes will be included as statistical covariates in all multivariate outcome analyses associated with Specific Aims 1a-1c, and will additionally be included in exploratory sub-group analyses to test for moderating effects on treatment response and/or contingent effects among subsets of participants. Primary outcome analyses for Specific Aims 1a, 1b, and 1c will be carried out using mixed effects Generalized Linear Model (GLM) equations.

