8.3 HIV Sexual Risk Behavior

HIV sexual risk behavior outcomes will be assessed at all time points throughout the study, and will be operationalized dichotomously (e.g., incident STI via biomarker testing), as a counted variable (e.g., number of days/times engaged in CAI in the past 30 days), and as a continuous variable (e.g., a HIV risk severity index generated from multiple factor-analyzed items). Power calculations for engagement in HIV sexual risk behaviors assume a 65% probability of engagement during the pre-intervention period for participants in the DD arm (equivalent to ~2:1 odds of engagement). Multivariable inferential analyses of dichotomous outcomes will take the form of GLMs employing the Bernoulli family and logit link function; counted outcomes will be analyzed with GLMs employing the Poisson-log or negative binomial link functions as distributional patterns dictate (note: if data evidence an over-representation of zeros or an overdispersion of variance, zero-inflated Poisson and/or negative binomial analyses may be substituted); continuous outcomes will be analyzed using GLMs employing the identity link and Gaussian family functions and assume a single covariate unless otherwise stated (note: iteratively reweighted, bootstrapped, or jack-knifed estimation procedures may be used in Gaussian models if sensitivity analyses indicate undue influence from outliers). Mixed effects GLM models are considered the best linear unbiased estimators for repeated measures data employing non-parametric and/or limited dependent variables. All power calculations are premised on tests of association across two time points (e.g., baseline with app completion; app completion with brick-and-mortar program completion), providing the most conservative estimate of minimum detectable effect (MDE) size estimations; all power calculations assume $\alpha \leq 0.05$ (two-tailed), and $1 - \beta = 0.80$.

Table 2: Instruments, Targets, Variable Operationalizations, and Minimum Detectable Effects

Table 2: Instruments, Targets, Variable Operationalizations, and Minimum Detectable Effects (1 - β = 0.80; α = 0.05, two-tailed)

Instrument	Target	Variable Operationalizations			Power-- Minimum Detectable Effects		
		Dichotomous (Di)	Count (Cu)	Continuous (Co)	Model 1— RCT (Aim 1a; n=150/n=150)	Model 2— Tx Effects (Aim 1b; N = 300)	Model 3— Matched Comparison (Aim 1c; N = 300/N ~ 600)

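### Aim 1c is called non-inferiority, but no margin, decision rule, outcome or time point is set, and its stated power is for detecting a difference

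*Combined protocol and SAP*

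**What the plan says.** The combined protocol and SAP applies the label in three places.

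- Section 2.1 promises efficacy and "non-inferiority in a scientifically rigorous randomized trial".
- Figure 1 in section 3.1 labels Aim 1c "Non-inferiority Trial - A historical matched comparison design to evaluate the outcomes".
- The Aim 1c part of section 9.2 (two sections carry that number) states: "Aim 1c provides a non-inferiority trial against the group-based, brick-and-mortar intervention upon which the app is based".

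On method, section 9.2 adds only this: "The proposed analytical model allows for non-inferiority analyses comparing the relative efficacies of brick-and-mortar vs. mHealth delivered intervention content". The sole analysis named is the mixed effects GLM that section 8.1 assigns to all three aims: "Primary outcome analyses for Specific Aims 1a, 1b, and 1c will be carried out".

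On power, section 8.3 says: "All power calculations are premised on tests of association across two time points", with two-tailed alpha 0.05 and 80% power. It gives "app completion with brick-and-mortar program completion" as an example of such a pairing. Section 9.2 and Table 2 then list minimum detectable effects for 300 app users against about 600 historical participants. For the dichotomous outcomes these are OR 1.52 (continuum), 0.62 (methamphetamine use) and 0.66 (sexual risk).

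Section 1.1.3, the formal statement of Aim 1c, describes a historical matched comparison and does not mention non-inferiority.

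**The concern.** Non-inferiority is a claim that the new delivery is not worse than the old by more than a stated amount. Without that amount there is no null hypothesis to reject and no bound to compare with a confidence limit. The plan also covers three outcome domains, each operationalised in several ways and measured repeatedly, and does not say which would carry the conclusion.

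The analysis as written is a two-tailed difference test. It can show the app better, show it worse, or show neither. The third result is the dangerous one: under a non-inferiority label it is easily reported as success, although failing to find a difference does not exclude a meaningful deficit. A margin chosen after the data are seen could decide the conclusion.

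**Working it through.** **Inputs.** From section 9.2: 300 app and about 600 historical participants. From sections 8.2 and 8.3: base rates of 30% (continuum), 80% (methamphetamine use) and 65% (sexual risk). The last two are defined for the delayed arm before intervention. From section 8.3: two-tailed alpha 0.05 and power 0.80. The margins below are my assumptions, because the plan gives none.

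**Step 1: what the stated effects are.** Take the continuum outcome with the historical group at 30%.

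- OR 1.52 gives odds 0.4286 × 1.52 = 0.651, a rate of 39.4%, and a difference of 0.0945.
- The pooled rate is 0.3315, so the null SE is √(0.3315 × 0.6685 × (1/300 + 1/600)) = 0.0333.
- The SE under the alternative is √(0.30 × 0.70/600 + 0.394 × 0.606/300) = 0.0339.
- Power = Φ[(0.0945 − 1.96 × 0.0333)/0.0339] = Φ(0.86) ≈ 80.6%.

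The same formula for all three outcomes:

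| Outcome | Stated OR | Power, historical arm at base rate | Power, app arm at base rate |
|---|---|---|---|
| Continuum, 30% | 1.52 | 80.6% | 79.9% |
| Use, 80% | 0.62 | 82.8% | 81.7% |
| Sexual risk, 65% | 0.66 | 82.1% | 81.7% |

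One-sided alpha 0.05 would give about 1.45-1.47, 0.64-0.66 and 0.69-0.70, which do not match. The continuous effect for N = 900 comes to f² = 0.0087, which rounds to the stated 0.01. The stated figures are therefore two-tailed difference-test effects with no margin in them. I did not check the count-outcome figures, because the plan gives no base rates or dispersion for them.

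**Step 2: non-inferiority power by margin.** Assume no true difference and require the 95% confidence limit to exclude margin m:

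power = Φ[m / √(p(1−p)(1/300 + 1/600)) − 1.96], where 1/300 + 1/600 = 0.005.

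At p = 0.80 the SE is √(0.16 × 0.005) = 0.0283. For m = 0.05 the power is Φ(1.768 − 1.96) = 42%.

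| Base rate | SE | Power, m = 5 points | Power, m = 10 points | Margin giving 80% power (2.80 × SE) |
|---|---|---|---|---|
| 30% | 0.0324 | 34% | 87% | 9.1 points |
| 65% | 0.0337 | 32% | 84% | 9.4 points |
| 80% | 0.0283 | 42% | 94% | 7.9 points |

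**Step 3: numbers needed at 1:2.** App n = (1.96 + 0.84)² × p(1−p) × 1.5/m². At 30%, 65% and 80% this gives 989, 1,072 and 754 for 5 points, and 248, 268 and 189 for 10 points.

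**Step 4: margins the size of the stated effects.** On the log-odds scale SE = √(0.005/(p(1−p))). Taking the reciprocals of the stated ORs as if they were margins:

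- Continuum: Φ(0.419/0.154 − 1.96) ≈ 77%.
- Use: Φ(0.478/0.177 − 1.96) ≈ 77%.
- Sexual risk: Φ(0.416/0.148 − 1.96) ≈ 80%.

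**Step 5: why non-significance is not enough.** This is an edge case, not a forecast. With historical use at 80%, an app OR of 1.459 (use 85.4%) has SE √(1/(600 × 0.16) + 1/(300 × 0.854 × 0.146)) = 0.193. It sits just at non-significance, since ln 1.459 = 1.96 × 0.193. Its upper 95% limit is 1.459² ≈ 2.13, or 89.5% use against 80%.

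**The case against.** The strongest reply is that the sample may be adequate. Step 4 supports it: at margins the size of the stated effects, non-inferiority power would be 77-80%. A reader might infer from the 5-point column that the comparison is underpowered. The documents do not support that, because they favour neither 5 nor 10 points. The planned covariate-adjusted mixed models could also change the precision. What stands is that adequacy cannot be judged until a margin exists. The reciprocals in Step 4 show precision only and do not justify a margin.

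Three other inferences go too far.

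- A reader might think two-tailed alpha 0.05 is itself wrong. It is not: a two-sided 95% interval serves a non-inferiority test at one-sided 0.025.
- A reader might object that the completion pairing is mismatched, since "participants in both arms will be given 30-days to complete the 24 sessions" while section 2.2.4 describes an 8-week group programme. Completion against completion aligns the two by treatment phase, and different calendar lengths are not in themselves an error. The fair point is that section 8.3 offers the pairing only as an example.
- A reader might take the wording of section 2.1 as hiding a non-randomised design. Sections 1.1.3, 3.1 and 9.2 disclose the historical comparison, so section 2.1 is loose wording.

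It can also be said that non-inferiority is absent from the formal aim, that section 8.1 may mean analyses of primary outcomes rather than a ranking of aims, and that Aims 1a and 1b are unaffected. All this is fair and limits the reach of the point. It does not supply a criterion for a conclusion that Figure 1 and section 9.2 announce.

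**Conclusion.** The point holds. The plan names a non-inferiority conclusion for Aim 1c but gives no margin, no rule, and no designated outcome or time point, and its 80% power belongs to a different hypothesis. This part needs no assumed figure.

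The size of any shortfall is unknown. The range of 32-42% to 84-94% rests on my assumed margins, true equality, independent groups at one time point, no attrition or matching loss, and the plan's base rates. The plan gives no rate at group-programme completion and no retention allowance. If 240 app users were retained (an assumed 20% loss) against 600, the same formula gives 28-37% for 5 points and 78-91% for 10 points.

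**What to change.** Choose one of two routes before any Aim 1c outcome comparison is run.

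1. **Keep the claim.** Name the outcome(s) and time point. Set a margin justified against the group programme's effect, not derived from the sample size. State that non-inferiority is concluded only if the relevant 95% confidence limit excludes the margin. If more than one outcome is used, add a multiplicity rule or require success on all of them. Restate the Aim 1c power for that margin, preferably with post-programme rates and expected retention. The cost is new analysis and power text. More participants may or may not be needed: about 754-1,072 app users for a 5-point margin, 189-268 for 10 points.

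2. **Drop the claim.** Delete non-inferiority for Aim 1c in sections 2.1, 3.1 (Figure 1) and 9.2. Report the difference with its 95% confidence interval as a non-randomised historical matched comparison, consistent with section 1.1.3. The cost is wording in three places and a weaker claim. This route remains open if the numbers under route 1 are out of reach.

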6.3 Enrollment Procedures

After the Informed Consent Form for the study has been read, any questions have been answered, the informed consent quiz has been passed, and the participant has electronically signed the consent form, a Research Coordinator or RA will deliver the baseline assessment, which takes approximately 60-90 minutes. To maximize accurate disclosure of high-risk and sensitive behaviors, data is collected via an audio computer-assisted self-interview (ACASI). Studies have demonstrated that disclosure rates of perceived stigmatized behaviors are increased through ACASI assessments. After the ACASI is completed, participants will be instructed to download the *Getting Off* app on to their smartphone. Once access to the app is granted (determined by randomization), participants will have 30-days to complete the 24 sessions.

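### Aim 1c selects historical comparators on having attended the group programme but counts every randomised app participant, so the two sides of the non-inferiority comparison enter under different rules

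*Combined protocol and SAP*

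**What the plan says.** Section 1.1.3 sets the app against "a matched sample of participants having previously attended the brick-and-mortar group-based" intervention. Section 9.2 (Specific Aim 1c Analysis) repeats that rule: app data are "contrasted against historical data from participants who have attended the brick-and-mortar Getting Off intervention after 2012", about 600 men, "matched according to age, race/ethnicity, and HIV status [see Random Assignment"]. Neither section says how many sessions count as attending, or whether a man's record begins at intake or at his first session.

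The app side in the same section is "pooled data from the proposed study (i.e., ID+DD, N=300"), that is, everyone randomised. Section 3.1 calls the design intent-to-treat, and "participants will be assessed regardless of participation or retention". Section 6.3 has participants download the app at baseline and then states: "Once access to the app is granted (determined by randomization), participants will have 30-days to complete the 24 sessions". Nothing requires a session to be opened.

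Section 8.3, in its text on power, gives "app completion with brick-and-mortar program completion" as an example of the two time points being compared.

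**The concern.** Attendance happens after a man enters the programme. Selecting on it removes those who signed up and never came, if the records contain such men. No equivalent selection is made on the app side. Engagement with treatment often goes with better outcome, so one side may be enriched for it and the other not. The three matching variables are fixed at baseline and do not touch this.

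The stake is the non-inferiority conclusion. Section 9.2 wants to compare the efficacy of two ways of delivering the same content. With misaligned entry, part of any observed difference reflects who was counted, and an app that works equally well in those who use it could fail to show non-inferiority.

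**Working it through.** **1. The plan's own figure, to see who is counted.** Inputs: 300 app and about 600 historical participants (9.2, Aim 1c); two-sided alpha 0.05 and 80% power (8.3); base rates of 30% for continuum advancement and 80% for methamphetamine use (8.2) and 65% for sexual risk (8.3); detectable odds ratios of 1.52, 0.62 and 0.66 (9.2, Aim 1c).

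Method: p2 = odds/(1 + odds), where odds = OR × p1/(1 − p1). Power = Φ[(|p1 − p2| − 1.96 × SE0)/SE1], with SE0 from the pooled proportion and SE1 from the separate proportions. The base rate is placed in the group of 300.

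| Outcome | p1 | OR | p2 | Power |
|---|---|---|---|---|
| Continuum | 0.30 | 1.52 | 0.394 | 0.799 |
| Methamphetamine use | 0.80 | 0.62 | 0.713 | 0.817 |
| Sexual risk | 0.65 | 0.66 | 0.551 | 0.817 |

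For methamphetamine use: SE0 = 0.0309, SE1 = 0.0296, and (0.0874 − 1.96 × 0.0309)/0.0296 = 0.90, so power is 0.817. With the base rate in the group of 600 instead, the three powers are 0.806, 0.828 and 0.821. The stated effects therefore reproduce from all 300 against 600, with no reduction for non-starters or non-completers. They are difference calculations and contain no margin.

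**2. Effect of app non-start when the app is equally effective.** The documents give no non-start rate and no post-treatment use rate, so these are assumptions. Starters have 50% use on both sides. Non-starters stay at 80%, the plan's pre-intervention rate. A share f of app participants never start, and the comparator contains attenders only.

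App use = (1 − f) × 0.50 + f × 0.80. The odds ratio is against 0.50.

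- f = 0.10: 0.45 + 0.08 = 0.53; OR = 0.53/0.47 = 1.13
- f = 0.20: 0.40 + 0.16 = 0.56; OR = 0.56/0.44 = 1.27
- f = 0.30: 0.35 + 0.24 = 0.59; OR = 0.59/0.41 = 1.44

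That is an apparent deficit of 3, 6 and 9 percentage points. If starter use is 60% or 40% instead, f = 0.20 gives an OR of 1.19 or 1.38. If both sides carry the same non-start share, or both are limited to starters, the OR is 1.00.

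**3. What this could do to a non-inferiority test.** The plan states no margin. For illustration only, take OR 1.61, the inverse of its detectable 0.62. Power = Φ[(ln 1.61 − ln OR)/SE − 1.96], where ln(1/0.62) = 0.478 and SE² = 1/(300 × pA × (1 − pA)) + 1/(600 × 0.50 × 0.50), with pA the app use rate.

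| Non-start f | OR | SE | Power |
|---|---|---|---|
| 0 | 1.00 | 0.1414 | 0.922 |
| 0.10 | 1.13 | 0.1416 | 0.715 |
| 0.20 | 1.27 | 0.1421 | 0.385 |
| 0.30 | 1.44 | 0.1430 | 0.123 |

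**4. The same test among starters on both sides.** The app sample falls to 300 × 0.90 = 270, 300 × 0.80 = 240 or 300 × 0.70 = 210. The OR is 1.00, the SE is 0.1466, 0.1528 or 0.1604, and power is 0.903, 0.879 or 0.846. The loss from the smaller sample is small beside the loss in step 3.

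**The case against.** Five arguments can be made for the plan.

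- *Attended is undefined and may simply mean enrolled.* This stands as a limit. A reader might infer that men with intake only are known to be excluded. That is the plain reading of the word, but no section says it or describes the programme records. If records start at intake, the gap shrinks.
- *Section 8.3 does not restrict anyone to completers.* Correct. A reader might infer a completer-against-completer analysis, but the phrase is an example of a time point in text about power, and step 1 shows that the sample sizes stay at 300 and about 600. The wording needs clarifying only.
- *The direction of bias is not established.* This stands in part. Eligibility needs only use within the past 365 days (5.1.2), and randomisation balances a stratum that includes action/maintenance (6.4), so some non-starters may already have stopped. The site's outpatient treatment serves treatment-seeking men (4.0), who may enter with heavier use. App participants also pass hurdles: a site visit, a consent quiz and a baseline of 60 to 90 minutes.
- *The pilot does not supply a non-start rate.* Correct. In 2.2.5, 12 of 15 finished all eight sessions. The other 3 (20%) did not finish, which is not the same as never starting. Group attenders who later drop out also stay in an attended cohort.
- *Section 8.1 plans covariate adjustment beyond the matching variables, including readiness for change.* It may reduce imbalance where the historical records hold those variables, but it cannot restore non-attenders who were never in the comparator.

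**Conclusion.** The entry rules of Aim 1c are misaligned as written: attendance on one side, randomisation on the other. No matching variable, covariate or analysis set in the plan aligns them. This should be corrected before the two sides are compared, because a filter chosen later could decide the result.

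The size cannot be computed from the documents. Under the stated assumptions (50% use in starters, 80% in non-starters, equal efficacy, no non-starters in the comparator), 10% to 30% non-start gives an OR for use of 1.13 to 1.44 against an equally effective app. The power figures rest further on an assumed margin.

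A reader might conclude that non-starters are known to count against the app alone and that Aim 1c is biased one way on every outcome. The documents do not support that. Bias against the app is the likely direction if non-starters do worse, but it is not certain.

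**What to change.** In 1.1.3 and 9.2 (Aim 1c), state one entry point and one time zero for both sides.

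- **Where programme records with outcomes exist from intake:** take all men admitted after 2012, timed from intake, whatever their attendance, and compare them with all app participants timed from app access.
- **Where they do not:** keep the all-randomised app analysis. Add a pre-specified comparison of app participants who opened at least one session with group participants who attended at least one session, labelled as a comparison among starters. Report the share of app participants who never started.
- **In 8.3:** say that completion means the end-of-programme time point, not a population of completers.

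The cost is wording, an extraction rule for existing programme records, and use of the app's backend data. No new participants are needed. The intake version depends on records that the documents do not describe. The fallback limits its conclusion to starters and uses a somewhat smaller app sample (270 to 210 at 10% to 30% non-start). Neither option removes the difference between treatment-seeking and outreach-recruited men, which should be reported as a remaining limitation.
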